### 11.9 Analysis of Safety Data

Safety data such as BCDVA, slit lamp findings, and fundus findings will be summarized descriptively (mean, standard deviation, minimum, and maximum for continuous outcomes, and counts and percentages for categorical outcomes) for primary and all eyes.

For IOP at each visit, the mean, standard deviation, minimum and maximum and change from baseline will be summarized for all implanted eyes. Additionally, number and percentage of eyes with a IOP change from baseline of “decrease > 10 mmHg”, “decrease  5 mmHg to ≤ 10 mmHg”, “change within ± 4 mmHg”, “increase 5 mmHg to ≤ 10 mmHg”, and “increase > 10 mmHg” will be prepared for each study visits.

Manifest spherical equivalence (MRSE) will be summarized descriptively with the 95% confidence interval for the mean for primary eyes and all eyes at each visit. Additionally, the same analyses will be performed on the MRSE adjusted by normal aging (i.e., minus 0.082 D per year).

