### **11.7 Baseline Demographic Characteristics**

Demographic data including, but not limited to, age, race, sex and ethnicity and baseline characteristics including, but not limited to, DCNVA, UCNVA, UCDVA, BCDVA, manifest refraction spherical equivalent (MRSE), cycloplegic refraction spherical equivalent (CRSE), will be reported for each subject. Baseline characteristics such as age, sex, race, and near visual acuity will be summarized.

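### Section 11.9 gives a confidence interval for the mean MRSE at each visit but, in the visible text, none for the within-eye change from baseline that the aging correction is meant to isolate

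*Combined protocol and SAP*

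**What the plan says.** In the combined protocol and SAP, section 11.9 (Analysis of Safety Data), MRSE is to be "summarized descriptively with the 95% confidence interval for the mean for primary eyes and all eyes at each visit". The plan adds that "the same analyses will be performed on the MRSE adjusted by normal aging", where the adjustment is "minus 0.082 D per year".

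The paragraph before it treats IOP differently: "For IOP at each visit, the mean, standard deviation, minimum and maximum and change from baseline will be summarized for all implanted eyes". It also plans counts of eyes in five categories of IOP change.

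The data for a paired MRSE analysis are already planned. Under section 11.7, baseline "manifest refraction spherical equivalent (MRSE), cycloplegic refraction spherical equivalent (CRSE), will be reported for each subject". Table 1 in section 8.2 schedules manifest refraction preoperatively and from 1 month onward; at 1 week a footnote refers back to the baseline refraction.

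The visible text sets no hypothesis, margin or SD for MRSE. Section 11.10 rules out p-values where no hypothesis was pre-specified. Parts of section 11.10 are redacted.

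**The concern.** Subtracting a yearly drift makes sense only if the reader wants to know how far refraction has moved since some starting point, beyond what aging would produce. The planned interval instead describes where the group mean lies at a visit. Three things are missing.

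- **An interval for the shift.** It cannot be built from the baseline interval and a visit interval without the within-eye correlation, which the plan does not report.
- **The distribution of change across eyes.** Shifts in opposite directions cancel in a visit mean, so a few eyes with large changes may not show.
- **A fixed set of eyes.** As follow-up falls, the baseline mean and a later visit mean come from different eyes, and their difference mixes change with composition.

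At stake is how clearly the refractive effect of the procedure is reported in the safety section. No success criterion depends on it.

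**Working it through.** The plan states no precision figure for MRSE, so there is none to reproduce.

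**Inputs from the documents**
- Aging drift of 0.082 D per year (section 11.9), which is 0.041, 0.082, 0.123 and 0.164 D at 6, 12, 18 and 24 months.
- Cohort of 360 with 10% dropout by 12 months (section 11.3): 360 × 0.90 = 324 eyes. Section 11.3 itself names 330 available eyes; using 330 changes the half-widths by under 1%.
- Entry range for MRSE of −0.75 to +0.50 D (section 7.5.1). The width is 1.25 D, and a uniform spread would give SD = 1.25/√12 = 0.36 D.

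**Assumptions, not in the documents**
- SD 0.30 D at both visits (range 0.25 to 0.50 D shown below).
- Within-eye correlation r of 0.5, 0.7 or 0.8.
- Lost eyes differ from retained eyes by 0.15 D at baseline.

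**95% half-widths, SD 0.30 D, n = 324**
- Planned visit-mean interval: 1.96 × SD/√n = 1.96 × 0.30/18 = 0.033 D.
- Two visit means compared as if independent: 1.96 × SD × √(2/n) = 0.046 D.
- Paired change: 1.96 × SD × √(2(1 − r)/n), which gives:

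| r | Paired half-width (D) |
|---|---|
| 0.5 | 0.033 |
| 0.7 | 0.025 |
| 0.8 | 0.021 |

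The paired interval is narrower than the planned visit-mean interval only when √(2(1 − r)) < 1, that is, when r > 0.5. It is narrower than the independent comparison for any r > 0.

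**Sensitivity to SD (n = 330)**

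| SD (D) | Visit mean | Two means as independent | Paired, r = 0.5 | Paired, r = 0.8 |
|---|---|---|---|---|
| 0.25 | 0.027 | 0.038 | 0.027 | 0.017 |
| 0.36 | 0.039 | 0.055 | 0.039 | 0.025 |
| 0.50 | 0.054 | 0.076 | 0.054 | 0.034 |

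**Changing set of eyes.** The mean of the retained eyes differs from the mean of all eyes by (fraction lost) × (lost minus retained difference) = 0.10 × 0.15 = 0.015 D, with no eye changing. That is 0.015/0.082 = 18% of one year's aging term. Within-eye change in eyes measured at both times removes this component.

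**The case against.** The strongest reply is that the planned summary already comes close to the target. When the same eyes attend both visits, the difference between the two means equals the mean within-eye change exactly, and subtracting the aging term moves the visit mean by a known amount. A reader might infer that the plan cannot detect a refractive shift at all. The documents do not support that: even two means compared as independent give a half-width of 0.046 D (0.038 to 0.076 D over the SD range), below the 12-month aging term of 0.082 D. This part of the reply stands.

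A reader might also take the ratio of the independent to the paired interval, 1/√(1 − r) = 1.4 to 2.2 for r from 0.5 to 0.8, as precision that the plan gives up. That overstates the loss, because section 11.9 specifies an interval for one visit mean and no independent two-visit comparison.

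Other limits are fair. MRSE is not in the section 7.4 list of safety attributes, it carries no hypothesis or margin, and the redacted parts of section 11.10 may hold further refraction analyses. Pairing also does not cure informative dropout: if the eyes that shifted are the ones that fail to return, the paired mean is biased too.

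What remains is narrower. The visible text gives no interval for the shift and no spread of per-eye change, and its visit means can move because different eyes are seen.

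**Conclusion.** The point holds as a minor, inexpensive improvement to a descriptive safety summary, limited to the visible text. The plan corrects MRSE for elapsed aging but attaches its interval to the level at each visit, so the shift beyond aging has no stated uncertainty. The composition artefact is about 0.015 D at the plan's own 10% dropout and an assumed 0.15 D difference. The precision gain over the planned visit-mean interval runs from none at r = 0.5 (0.033 D in both cases) to 0.021 against 0.033 D at r = 0.8, and rests on the assumed SD and correlation. Below r = 0.5 the paired interval is the wider of the two, but it is still the one that describes change. The case for pairing rests first on answering the right question and only second on precision. Neither Objective #1 nor Objective #2 is affected.

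**What to change.** In section 11.9, add that at each visit with a manifest refraction, for eyes measured at both baseline and that visit, the within-eye change in MRSE from baseline will be summarized (mean, SD, minimum, maximum) with a 95% CI for the mean change. Report it raw and after subtracting 0.082 D × years since baseline, for primary eyes first and then all eyes. Naming baseline as the time origin also settles from when the years are counted, which the visible text leaves open. Keep the visit means as descriptive, and show the number of eyes contributing at each visit. Counts of eyes by size of change, as already planned for IOP, would be a useful optional addition. A note should say that the paired summary does not correct for eyes that shifted and did not return.

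The cost is one SAP sentence and one table. It needs no new data.

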## **12.0 STUDY MONITORING**

Sponsor or CRO personnel will monitor all clinical studies in accordance with FDA guidelines. Study monitoring will involve the following elements:

- Sponsor or CRO personnel will meet with Investigators prior to the initiation of the study in order to review the adequacy of the facility, equipment and clinical personnel with respect to the needs of the study and to familiarize the Investigator and clinic staff with the protocol.
- Sponsor or CRO personnel will meet with Investigators and clinic staff at initiation of the time of study to ensure that subjects are being properly consented, the protocol examination methods are being complied with and that study data is being properly recorded.
- Sponsor or CRO personnel will meet with the Investigator and clinic staff at any time during the study regarding study conduct to ensure ongoing compliance with the protocol and data recording requirements.
- Sponsor or CRO personnel will maintain ongoing email and telephone communication with the Investigator and clinic staff regarding study conduct.
- The CRO shall select, train and manage qualified contract personnel to visit each Investigational site to review and monitor source documents and electronic data in accordance with FDA guidance.

## **APPENDIX 1: EXAMINATION METHODS**

Refractions and acuity measurements shall be obtained by an ophthalmologist, optometrist or trained technician (who is supervised directly by the ophthalmologist or optometrist).

### **Manifest Refraction**

Manifest refraction will be performed pre and post-operatively using ETDRS acuity charts and standard phoropters. All systems will employ actual or equivalent optical distances of at least 4 meters (13 feet) and ambient lighting will be adjusted based on chart specifications. Chart luminance will fall within the ANSI required range of 80-160cd/m^2 and chart contrast will be a minimum of 85%.

### **Cycloplegic Refraction**

Cycloplegic refraction will be performed ~ 20 minutes after application of 1 drop of tropicamide 1% at select pre and post-operative visits using the same systems as for manifest refraction.

### **Instrument for Measuring Visual Acuities**

All visual acuities will be measured via the OPTEC 6500 (Stereo Optical, [name] USA [name] or [name]). This system utilizes a lens system to simulate various test distances for distance, intermediate and near. The Optec 6500 has a microprocessor controlled internal illumination system that results in constant luminance of 85cd/m^2; therefore, normal ambient lighting may be used as lighting conditions are not a factor in the testing set up. The manufacturer's instructions for use will be provided to each Investigational site.

#### **Distance Visual Acuity**

Distance visual acuity will be measured at a simulated (optical) distance of 20 feet.

#### **Intermediate Visual Acuity**

Intermediate visual acuity will be measured at a simulated (optical) distance of 66cm.

#### **Near Visual Acuity**

Near visual acuity will be measured at a simulated (ocular) distance of 40cm.

#### **Determination of Near Add**

The add power will be determined by adding plus lenses, using the Optec 6500 at a simulated distance of 40cm.

#### **Determination of Dominant Eye**

The subject will be advised to perform the following steps for determination of the dominant eye.

1. Hold your hands at arm's length out in front of you. Your palms should be pointing forward - in other words, you should be looking at the backs of your hands.
2. Make a "triangle." Extend both of your thumbs so that they're roughly perpendicular to the rest of the hand. Overlap your hands so that the space between makes a triangle. Your two

thumbs should be at the bottom of the triangle, while the edge and index finger of each hand form the two remaining sides.

3. The triangle space between your hands acts as a viewing window - you should be able to clearly see objects through it.
4. Look at an object through the triangle hole made by your hands with both eyes open. Find a nearby object that's small enough (or far enough away) that you can see the whole object through the viewing window between your hands. This can be anything - a door knob, a coffee mug, or even a letter on a faraway billboard.
5. Focus on the object. Try to focus your eyes on the object between your hands - not your hands themselves. Your hands should become somewhat blurry, while the object remains clear and in-focus. It's important to line this object up directly in front of you and to stare straight at it - turning your head to either side can distort your results.
6. For best results, at this point, make minor adjustments to your hands so that the object you're looking at fits almost exactly within the edges your viewing window. In other words, if your triangle is bigger than the object you're looking at, move your hands together to make it smaller, and vice versa.
7. Alternate closing each eye to see which gives better vision. Close one eye, then open it and close the other. Each time you switch eyes, the object you're looking at should do one of two things. It should either become obscured behind one of your hands *or* remain visible. Next, try your other eye. Your dominant eye is the one that allows you to see the object while it remains open.

### **Scleral Thickness Measurement**

Scleral thickness will be measured and printed using the Sonomed Ultrasonic Biomicroscope (UBM). The manufacturer's instructions for use will be provided to each Investigational site.

### **Pupil size, shape and reaction**

The NeurOptics Pupillometer is a portable, battery-operated, hand-held device used to measure the iris' reaction to a standardized level and duration of light. The manufacturer's instructions for use will be provided to each Investigational site.

The pupils of both eyes will be assessed at each and every visit as follows:

- Round
- Elliptical
- Irregular

## **Slit Lamp Evaluation – Grading**

### **Lids / Lashes**

Blepharitis (using the Efron Grading scale and reference drawings):

- 0 = none
- 1 = trace (1+)
- 2 = mild (2+)
- 3 = moderate (3+)
- 4 = marked / severe (4)

Meibomian Gland Dysfunction (using the Efron Grading scale and reference drawings):

- 0 = none
- 1 = trace (1+)
- 2 = mild (2+)
- 3 = moderate (3+)
- 4 = marked / severe (4)

### **Cornea**

Superficial punctate keratitis (using the Efron Grading scale and reference drawings):

- None
- Mild
- Moderate
- Marked or Severe

Corneal abrasion:

- None
- Tiny
- 1-2mm
- 2-3mm
- > 3mm

Corneal edema (using the Efron Grading scale and reference drawings):

- 0 = no evidence of corneal edema
- 1 = trace corneal edema (edema involves 0% to 5% of the cornea)
- 2 = mild corneal edema (edema involves 5% to 25% of the cornea)
- 3 = moderate corneal edema (edema involves 26% to 50% of the cornea)
- 4 = marked/severe corneal edema (edema involves > 50% of the cornea)

Corneal endothelial gutatta:

- 0 = no corneal gutatta
- 1 = rare corneal gutatta
- 2 = few corneal gutatta
- 3 = many corneal gutatta
- 4 = marked/severe corneal gutatta with stromal edema and bullous lesions
- Other abnormal corneal findings (specify)

## Conjunctiva

Conjunctiva injection (using the Efron Grading scale and reference drawings):

- 0 = none
- 1 = trace (1+)
- 2 = mild (2+)
- 3 = moderate (3+)
- 4 = marked/severe (4)

Subconjunctival hemorrhage:

- 0 = none
- 1 = less than or equal to 1 quadrant
- 2 = 2 quadrants
- 3 = 3-4 quadrants

Conjunctiva edema:

- 0 = none
- 1 = trace
- 2 = mild
- 3 = moderate
- 4 = marked/severe

Other abnormal conjunctival findings (specify)

## Crystalline Lens

Crystalline lens pathology using the LOCSII scale (with reference photos as published in Archives of Ophthalmology July 1989) as follows:

- Normal
- Lens Opacity
- Other Abnormal Findings (specify)

If lens opacity, please complete the following:

- Nuclear/Color Opalescence:    N0    N1    N2    N3
- Cortical:                            C0    C1    C2    C3    C4
- Posterior Subcapsular:        P0    P1    P2    P3
- Anterior Subcapsular:          A0    A1    A2    A3

### Anterior Chamber

Cell and flare will be graded according to the SUN grading scheme (using a 1x1 mm slit lamp beam):

#### SUN Grading for AC Cells

GRADE	CELLS IN 1x1mm Field
0	<1
0.5+	1-5
1+	6-15
2+	16-25
3+	26-50
4+	50+

#### SUN Grading for AC Flare

GRADE	Description
0	None
1+	Faint
2+	Moderate (iris/lens details clear)
3+	Marked (iris/lens details hazy)
4+	Intense (fibrin/plastic aqueous)

#### Iris appearance

- 1 = Normal
- 2 = Abnormal (if abnormal, please describe)

**Intraocular Pressure**

Intraocular pressure will be measured using Goldmann applanation tonometry. Measurements will be taken according to the published guidelines set forth by Michael A. Kass [*Kass MA. Standardizing the measurement of intraocular pressure for clinical research. Guidelines from the Eye Care Technology Forum. Ophthalmology. 1996 Jan;103 (1):183-5*]. Copies of this guideline will be provided to all sites.

**Gonioscopy**

The angle will be evaluated using a 3 or 4 mirror lens and the following grading scheme:

- Grade 3 – 4 (Wide Open: Angle > 20 degrees < 45 degrees)
- Grade 2 (Moderately Narrow: Angle = 20 degrees)
- Grade 1 (Extremely narrow: Angle = 10 degrees)
- Grade 0 (Angles Closure: Angle + 0 degrees)
- Other: (Specify)

**A-Scan**

Axial length and ACD will be measured and recorded.

**Internal Examination**

**Peripheral Fundus Examination**

- Normal
- Abnormal (if abnormal, please describe)

**Cup to Disc Ratio** will be assessed by means of a dilated fundus exam using condensing lenses and the slit lamp biomicroscope.

**Other Observations:**

Photographs, drawings and / or standard descriptive ophthalmic terms may be used as needed to describe any other ocular findings.

[Redacted]

[REDACTED]

[REDACTED]

[REDACTED]

[REDACTED]

[REDACTED]

[REDACTED]

[REDACTED]

[REDACTED]

[REDACTED]

[REDACTED]

[REDACTED]

[REDACTED]

[REDACTED]

[REDACTED]  
[REDACTED]  
[REDACTED]

[REDACTED]  
[REDACTED]  
[REDACTED]

[REDACTED]  
[REDACTED]  
[REDACTED]  
[REDACTED]

[REDACTED]  
[REDACTED]  
[REDACTED]

[REDACTED]

[REDACTED]  
[REDACTED]  
[REDACTED]

[REDACTED]  
[REDACTED]

[REDACTED]

[REDACTED]

[REDACTED]  
[REDACTED]  
[REDACTED]

[REDACTED]  
[REDACTED]  
[REDACTED]  
[REDACTED]

[REDACTED]

[REDACTED]

[REDACTED]  
[REDACTED]  
[REDACTED]

[REDACTED]  
[REDACTED]  
[REDACTED]  
[REDACTED]

[REDACTED]

[REDACTED]  
[REDACTED]  
[REDACTED]

[REDACTED]  
[REDACTED]

[REDACTED]

[REDACTED]  
[REDACTED]

[REDACTED]  
[REDACTED]  
[REDACTED]

[REDACTED]  
[REDACTED]  
[REDACTED]  
[REDACTED]  
[REDACTED]  
[REDACTED]

[REDACTED]  
[REDACTED]  
[REDACTED]

[REDACTED]

[REDACTED]  
[REDACTED]  
[REDACTED]  
[REDACTED]

[REDACTED]  
[REDACTED]  
[REDACTED]  
[REDACTED]

[REDACTED]

[REDACTED]

[REDACTED]

[REDACTED]  
[REDACTED]

[REDACTED]

[REDACTED]  
[REDACTED]  
[REDACTED]

[REDACTED]

[REDACTED]

[REDACTED]  
[REDACTED]

[REDACTED]

[REDACTED]

[REDACTED]

[REDACTED]

[REDACTED]

[REDACTED]

[REDACTED]

[REDACTED]

[REDACTED]

[REDACTED]

[REDACTED]

[REDACTED]

[REDACTED]

[REDACTED]

[REDACTED]

[REDACTED]

[REDACTED]

[REDACTED]

[REDACTED]

[REDACTED]

[REDACTED]

[REDACTED]

[REDACTED]

[REDACTED]

[REDACTED]

[REDACTED]

[REDACTED]

[REDACTED]

[REDACTED]

[REDACTED]

[REDACTED]

[REDACTED]

[REDACTED]

[REDACTED]

[REDACTED]

[REDACTED]

[REDACTED]

[REDACTED]

[REDACTED]

[REDACTED]

[REDACTED]

[REDACTED]

[REDACTED]

[REDACTED]

[REDACTED]

[REDACTED]

[REDACTED]

[REDACTED]

[REDACTED]

[REDACTED]

[REDACTED]

[REDACTED]

[REDACTED]

[REDACTED]

[REDACTED]

[REDACTED]

[REDACTED]

[REDACTED]

[REDACTED]

[REDACTED]

[REDACTED]

[REDACTED]

[REDACTED]

[REDACTED]

[REDACTED]

[REDACTED]

[REDACTED]

[REDACTED]

[REDACTED]

[REDACTED]

[REDACTED]

[REDACTED]

[REDACTED]

[REDACTED]

[REDACTED]

[REDACTED]

[REDACTED]

[REDACTED]

[REDACTED]

[REDACTED]

[REDACTED]

[REDACTED]

[REDACTED]

[REDACTED]

[REDACTED]

[REDACTED]

[REDACTED]

[REDACTED]

[REDACTED]

[REDACTED]

[REDACTED]

[REDACTED]

[REDACTED]

[REDACTED]

[REDACTED]

[REDACTED]

[REDACTED]

[REDACTED]  
[REDACTED]  
[REDACTED]

[REDACTED]  
[REDACTED]  
[REDACTED]

[REDACTED]  
[REDACTED]

[REDACTED]

[REDACTED]  
[REDACTED]  
[REDACTED]  
[REDACTED]

[REDACTED]

[REDACTED]

[REDACTED]  
[REDACTED]  
[REDACTED]

[REDACTED]  
[REDACTED]

[REDACTED]  
[REDACTED]  
[REDACTED]  
[REDACTED]

[REDACTED]

[REDACTED]  
[REDACTED]  
[REDACTED]  
[REDACTED]  
[REDACTED]

[REDACTED]

[REDACTED]

[REDACTED]

[REDACTED]

[REDACTED]

[REDACTED]

## **1. INTRODUCTION**

This charter governs the Data Safety Monitoring Board (the “DSMB”) established by Refocus Group, Inc. (the “Sponsor”) for the prospective, multicenter clinical trial of the VisAbility Implant System for the improvement of near visual acuity in Presbyopic patients under Protocol VIS-2014 (the “Clinical Trial”). The charter describes; the role and responsibilities of the DSMB, its members, conduct of meetings, its access to data and the manner of communication with the Sponsor.

## **2. ROLE OF THE DSMB: RESPONSIBILITIES & FUNCTION**

The primary role of the DSMB will be to ensure subject safety during the conduct of the Clinical Trial.

The DSMB will periodically evaluate the conduct of the Clinical Trial, adverse events and related safety data, and efficacy data from the perspective of relative benefit. The DSMB will make recommendations to the Sponsor as follows.

The recommendations of the DSMB to the Sponsor may include:

Modification of the study protocol, subject to approval of FDA or the IRB as applicable.

Continuation of the study according to the protocol and any related amendments.

Modification of the manner of study conduct.

Discontinuation of the study (with provisions for orderly discontinuation in accord with good medical practice).

Discontinuation of enrollment into the study.

## **3. DSMB MEMBERSHIP**

### **3.1 Members**

The DSMB will consist of three members with at least two members being licensed ophthalmologists or optometrists. The names and contact information of the DSMB members are as shown in the Appendix and will be updated periodically as needed should changes in DSMB membership occur. A copy of each DSMB member's curriculum vitae, updated at least annually, will be maintained by the Sponsor and available upon request. DSMB members will not act as investigators or sub-investigators for the Clinical Trial and will have no involvement in the Clinical Trial outside their role on the DSMB. DSMB members may not participate in any other IDE clinical study of a presbyopia correcting surgical device or technique, other than studies of presbyopia correcting intraocular lenses, nor may DSMB members serve as a personal physician to any subject enrolled in the Clinical Trial.

### **3.2 Financial Disclosure and Conflict of Interest**

Each DSMB member must disclose any financial or other material interests which may create a potential conflict with respect to their role on the DSMB including, but not limited to, equity interests in the Sponsor. Members of the DSMB will be responsible for advising the Sponsor of any change in related financial interests.

The Sponsor will be responsible for deciding whether financial or material interests may impact a member's objectivity, and may ask a member to resign from the DSMB.

